3.0 Objectives

Aim 1: Test the effects of CBT-TS to increase initiation of psychosocial pain treatment among Veterans receiving opioid analgesics for chronic pain. *Hypothesis: Participants receiving CBT-TS will be significantly more likely to initiate psychosocial pain treatment than participants in the control condition.*

Aim 2: Test the effects of CBT-TS to increase retention in psychosocial pain treatment among Veterans receiving opioid analgesics for pain. *Hypothesis: Participants receiving CBT-TS will attend significantly more sessions of treatment during the 6-month follow-up period than participants in the control condition.*

Aim 3: Evaluate the effects of CBT-TS in improving pain and opioid outcomes.

Hypotheses: Participants receiving CBT-TS will have significantly (a) reduced pain severity and interference, (b) improved physical functioning, and (c) reduced opioid dose and risk of misuse compared to participants in the control condition.

Exploratory Aim: Explore the effects of CBT-TS in increasing the initiation of and retention to other non-pharmacological pain treatments among Veterans receiving opioid analgesics for chronic pain.

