Assessments and Intervention: Veterans who are eligible and agree to participate will go through the informed consent process with research staff. Those who agree to participate will be asked to schedule a time to complete a baseline assessment and randomized to the CBT-TS condition or control. Following the baseline assessment, participants will then be scheduled a convenient time to conduct their intervention session (lasting approximately 45 minutes for both the experimental and the control condition). All study activities will be conducted by telehealth. Follow-up assessment will occur 1-, 3-, and 6-months post-treatment. At the conclusion of the 6-month follow-up assessment, participants will complete an exit interview describing their experiences with the study. Participants will receive compensation for their participation in the study. The compensation amount will be based on the following:

Baseline Assessment	\$50
1-Month Post-Treatment Follow-Up Assessment	\$40
3-Month Post-Treatment Follow-Up Assessment	\$40
6-Month Post-Treatment Follow-Up Assessment	\$40

Therefore, the total compensation for completing all the study components would be \$170. Payments will be made via direct deposit, check, or debit card following each study procedure listed above. Participants who do not complete the entire study for any reason will receive compensation for the components that were completed per the above schedule of payments.

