5.5 Study Evaluations

Medical Record Review and Treatment Utilization Form (TUF). Treatment utilization will be assessed through medical record review. The measure can be found in the **Appendix**. CAPRI and Joint Longitudinal Viewer will be used to access medical records. These are used at every VAMC and regional office and are accessible from every VA site of care. We will abstract data related to treatment utilization and medications across VHA facilities, including types of service (e.g., CBT-CP, chiropractic care), dates of service, number of sessions, and type and dose of medications. Non-VA medications known to VA providers and non-VA treatment notes are also included in the medical record. This data will be abstracted as available. Treatment initiation of psychosocial pain treatment is defined as attending at least one session of CBT-CP, ACT, or MBSR. We will also utilize data extraction from the Corporate Data Warehouse (CDW) to initially capture treatment utilization from medical records to assist in the medical record review. CDW contains financial, enrollment, demographic, diagnostic, treatment utilization, and other data across Veterans from 1979 to present. For training of the medical record chart review, the research staff will code 12 charts unrelated to the study and then meet to discuss and resolve differences. During the review for the study, they will overlap on 10 charts to facilitate agreement and ongoing discussion of differences will be addressed as needed. Drs. [name] and [name] will make the final decisions.

We will also collect self-report data on non-VHA care not identified in the medical record. *Self-report data will be exploratory* to evaluate the extent to which treatment was utilized outside the VHA and will not be included in the analyses of the primary and secondary outcomes. Participants will be asked at baseline and each follow-up period whether they have initiated treatments and the number of sessions for each type of treatment they have attended since the previous assessment. We will ask participants to provide information about where the treatment was received, and type of treatment (e.g., CBT-CP, MBSR, chiropractic, acupuncture).

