Aim 2 Hypothesis: Participants receiving CBT-TS will attend significantly more sessions of treatment during the 6-month follow-up period than participants in the control condition. The outcome will be sessions of psychosocial pain treatment attended during the 6-month follow-up period. Analyses will be conducted using MRM within a multilevel modeling (MLM) framework as this method allows for appropriate modeling of the covariance matrix when measures are repeated over time and can easily account for normal, skewed, and categorical data. MRM will be used, including treatment condition, follow-up time (centered on 6-month follow-up), and a condition by time interaction term as predictors of number of sessions of treatment attended.

Aim 3 Hypotheses: Participants receiving CBT-TS will have significantly (a) reduced pain severity and interference, (b) improved physical function, and (c) reduced opioid dose and risk

of misuse compared to participants in the control condition. The outcomes will be pain severity, pain interference, physical functioning, opioid dose, and risk of misuse. MRM will again be used. Treatment condition, follow-up time (centered on 6-month follow-up), and a condition by time interaction term will be included as predictors as will the relevant baseline autoregressors. Additional secondary analysis to demonstrate treatment robustness will involve centering time at the 1-month and 6-month follow-ups, allowing for examination of treatment differences at these timepoints.

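### Aim 2 names a 6-month session total but models an undefined repeated count centred at month 6; if the counts are per interval, the condition coefficient is not that total

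*Combined protocol and SAP*

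**What the plan says.** Section 3.0 Objectives states the Aim 2 hypothesis: "Participants receiving CBT-TS will attend significantly more sessions of treatment during the 6-month follow-up period than participants in the control condition". Section 5.7 Data Analysis repeats it and defines the variable: "The outcome will be sessions of psychosocial pain treatment attended during the 6-month follow-up period". Read plainly, that is one number per participant.

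The same paragraph of section 5.7 then chooses a mixed model because it "allows for appropriate modeling of the covariance matrix when measures are repeated over time", "including treatment condition, follow-up time (centered on 6-month follow-up), and a condition by time interaction term as predictors of number of sessions". The Abstract gives the same model. For the waves, section 5.1 says "Follow-up assessment will occur 1-, 3-, and 6-months post-treatment".

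The data source is chart review, which under section 5.5 captures utilisation "including types of service (e.g., CBT-CP, chiropractic care), dates of service, number of sessions, and type and dose of medications". A per-interval, a cumulative or a total count can each be built from those records.

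For Aim 2 the plan does not state how the count at each wave is formed, which coefficient is the test, the distribution or link, the covariance, or any contrast that sums over waves. Re-centring time as a secondary analysis is described for Aim 3 only. The exploratory retention analysis adopts the Aim 2 approach.

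**The concern.** The hypothesis and the model may have different targets. With time centred at month 6 and a condition-by-time term, the condition coefficient is the fitted arm difference at the month-6 wave. Whether that equals the difference in 6-month attendance depends on a coding decision that the plan leaves open.

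If each wave counts only sessions since the last wave, the coefficient is dominated by months 3 to 6, and extra sessions in month 1 count against CBT-TS. The intervals are also unequal (1, 2 and 3 months), so the time slope partly reflects interval length. A real difference in attendance could then be shrunk or, in some patterns, reversed. If each wave holds a running total, the target is about right, but the three values are nested sums of the same sessions and repeated-measures modelling adds little. Two analysts following the text could report different Aim 2 results.

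**Working it through.** **1. The plan's own figure.** Section 5.7 raises N = 250 by 20%: 250 × 1.20 = 300, which reproduces. The stated 80% power for Aim 2 cannot be reproduced, because no numeric effect, SD, session rate or start time is given. For orientation, 125 per arm at two-sided 0.05 (sidedness is assumed) gives 80% power at a standardised difference of 0.354. That does not reveal which form of the count was simulated.

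**2. Weights.** Inputs: waves t = 1, 3, 6 (section 5.1) and linear time centred at 6 (section 5.7). Assumed: linear scale, complete data, independence or random-intercept covariance. The weight of wave i in the fitted month-6 value is 1/3 + (t_i − t̄)(6 − t̄)/Sxx, with t̄ = 10/3 and Sxx = 5.444 + 0.111 + 7.111 = 12.667.
- Month 1: 0.333 − 6.222/12.667 = −0.158
- Month 3: 0.333 − 0.889/12.667 = 0.263
- Month 6: 0.333 + 7.111/12.667 = 0.895

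**3. Per-interval counts.** Let s1, s2, s3 be the shares of the true 6-month difference in months 0–1, 1–3 and 3–6. Share recovered = −0.158·s1 + 0.263·s2 + 0.895·s3.
- Even by month (1/6, 2/6, 3/6): −0.026 + 0.088 + 0.447 = 51%
- 50/40/10%: −0.079 + 0.105 + 0.089 = 12%
- 60/30/10%: 7%
- 20/50/30%: 37%
- 0/30/70%: 71%

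If no interval difference is negative, the ceiling is 89.5%, reached only when every extra session falls in months 3–6.

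**4. Cumulative counts.** The wave values are s1, s1+s2 and 1, so the interval weights become −0.158 + 0.263 + 0.895 = 1.00, then 0.263 + 0.895 = 1.16, then 0.895. The same five patterns recover 100%, 105%, 104%, 105% and 97%.

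**5. Simulation.** All of these inputs are assumptions and none is in the documents: 125 per arm, initiation 15% versus 30%, 1–12 weekly sessions, start times as listed. The weights of step 2 were used with a robust standard error, over 3,000 replicates. Power is the share of trials significant in favour of CBT-TS. Each month-6 cell gives the share of the total difference recovered, then power.

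| Start (weeks) | Total difference; power | Per-interval month 6 | Cumulative month 6 |
|---|---|---|---|
| Both 0–4 | 0.98; 0.70 | 10%; 0.31 | 109%; 0.69 |
| Both 2–8 | 0.97; 0.70 | 30%; 0.52 | 111%; 0.70 |
| Both 4–16 | 0.98; 0.71 | 61%; 0.61 | 101%; 0.71 |
| Both 0–26 | 0.84; 0.68 | 60%; 0.57 | 99%; 0.66 |
| CBT-TS 0–4, control 0–26 | 1.11; 0.83 | −27%; 0.00 | 117%; 0.89 |
| CBT-TS 2–8, control 0–26 | 1.11; 0.84 | 6%; 0.08 | 120%; 0.91 |

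**6. Covariance.** With an unstructured covariance and linear time (2,000 replicates, same six scenarios), the cumulative estimate recovered 18%, 7%, 98%, 98%, −5% and −20% of the total. Cumulative coding alone is therefore not a full safeguard.

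**The case against.** The strongest defence is that the text fits a running count. The outcome is defined over the 6-month period and time is centred at month 6, where a cumulative count is the 6-month total. Under that reading and a random intercept the coefficient has essentially the right target, and the repeated structure is redundant rather than wrong. This stands. A reader might infer that the declared test fails to answer Aim 2; the documents do not support that, because they do not say that the counts are per interval.

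A reader might also take the section 5.5 wording "the number of sessions for each type of treatment they have attended since the previous assessment" as proof of per-interval coding. It describes participant self-report, which the same section says "will not be included in the analyses of the primary and secondary outcomes". It does not define the Aim 2 count.

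Nor can one infer that most of the effect will be missed. Even with per-interval counts, a steady or later effect keeps about 51% to 71%. A one-session intervention may plausibly act early, but the documents give no timing. Likewise, the share of participants with zero sessions is not in the plan; the simulation's 85% and 70% simply follow from its assumed initiation rates.

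Section 5.7 also says that the framework handles skewed data and allows alternative procedures before unblinding. With a log link and a constant rate ratio the loss would be smaller. Neither provision defines the count or the contrast.

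**Conclusion.** The point holds as a gap in specification with a conditional consequence. Aim 2 targets a 6-month total, the model's condition coefficient is a month-6 value, and the plan never connects them.

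If counts are per interval, the coefficient is not the total. On a linear scale with independence or a random intercept, it recovers about half under an even monthly effect and about 12% or 7% in the two patterns with 90% of the effect before month 3 and at least half in month 1. It can reverse sign if only CBT-TS participants start early. If counts are cumulative, it is near the total under a random intercept but can be far off under an unstructured covariance with linear time. The power figures illustrate this under assumed inputs and do not predict this trial's power.

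Section 6.0 describes retention as a secondary goal, so the Aim 1 result is unaffected. This is a cheap improvement that should be made.

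**What to change.** Define the Aim 2 outcome as each participant's total chart-documented CBT-CP, ACT and MBSR sessions over the 6-month window, with zeros included. Where withdrawal truncates the record, use log follow-up time as an offset. Non-VA records are abstracted only as available, so the SAP should say that the total covers documented sessions.

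Compare arms with one count model, such as negative binomial or log-link Poisson with robust variance, and report the rate ratio and the difference in mean sessions. A prespecified contrast summing the three interval counts is an acceptable alternative. Keep the time course over months 0–1, 1–3 and 3–6 as descriptive, allowing for interval length. Make the same change to the exploratory retention analysis, and settle the wording before unblinding.

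The cost is a small change of SAP wording and the loss of the modelled time trend as the main test. No new data, visits or participants are needed, because dates of service are already abstracted.

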Data Analysis: Aim 1 Hypothesis: A Cox Proportional Survival Analysis will be conducted to examine treatment initiation by the 6-month follow-up. Condition will be entered into the model as a predictor of whether a participant reported attending treatment by the 6-month follow-up. A secondary logistic regression analysis will be conducted to examine treatment initiation by the end of the 6-month follow-up using worst case imputation of missing outcome to test robustness of any effects. **Aim 2 Hypothesis:** The outcome will be sessions of psychosocial pain treatment attended during the 6-month follow-up period. Analyses will be conducted using MRM within a multilevel modeling (MLM) framework as this method allows for appropriate modeling of the covariance matrix when measures are repeated over time and can easily account for normal, skewed, and categorical data. MRM will be used, including treatment condition, follow-up time (centered on 6-month follow-up), and a condition by time interaction term as predictors of number of sessions of treatment attended. **Aim 3 Hypotheses:** The outcomes will be pain severity, pain interference, physical functioning, opioid dose, and risk of misuse. MRM will again be used. Treatment condition, follow-up time (centered on 6-month follow-up), and a condition by time interaction term will be included as predictors as will the relevant baseline autoregressors. Additional secondary analysis to demonstrate treatment robustness will involve centering time at the 1-month and 6-month follow-ups, allowing for examination of treatment differences at these timepoints.

List of Abbreviations

ACT – Acceptance and Commitment Therapy

ASSIST – Alcohol, Smoking, and Substance Involvement Screening Test

BHS – Beck Hopelessness Scale

CBT – Cognitive Behavioral Therapy

CoE – VISN 2 Center of Excellence for Suicide Prevention

COMM – Current Opioid Misuse Measure

CPG – Clinical Practice Guidelines

ITT – Intent-to-treat

MAR – Missing at random

MBQ – Medication Beliefs Questionnaire

MBSR – Mindfulness-based stress reduction

MCAR – Missing completely at random

MEDD – Morphine equivalent daily dose

OD – Opioid use disorder

PCS – Pain Catastrophizing Scale

PROMIS – Patient Reported Outcome Measures Information System

PSEQ – Pain Self-Efficacy Questionnaire

PTWS – Pain Treatment Willingness Scale

SEM – Structural Equation Modeling

SBIRT – Screen, Brief Intervention, and Referral to Treatment

TSK – Tampa Scale for Kinesiophobia

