Preliminary Analysis. For all variables, we will examine the distribution for potential nonnormality and outliers. If necessary, appropriate data transformations or alternative data analysis procedures (e.g., nonparametric, bootstrapping) will be used prior to data unblinding. Prior to outcome analyses, baseline demographic and outcome variables will be assessed for baseline equivalency. Categorical variables will be analyzed using chi-square tests; continuous variable differences will be assessed using pooled t-tests. Per missing data design (see **Missing Data**), if baseline differences are detected, these covariates will then be included in the final model as auxiliary variables to improve the plausibility of assuming data is MAR.⁹⁶

Primary Analyses in Support of the Specific Aims. **Aim 1 Hypothesis:** Participants receiving CBT-TS will be significantly more likely to initiate psychosocial pain treatment than participants in the control condition. Treatment initiation of psychosocial pain treatment will be treated as a binary outcome variable (0|1). A Cox Proportional Survival Analysis.⁹⁷ will be conducted to examine treatment initiation by the 6-month follow-up. This approach is like logistic regression except it accounts for missing data across the follow-up timepoints. Condition will be entered into the model as a predictor of whether a participant reported attending treatment by the 6-month follow-up. The assumption of proportionality will be tested in this model. A secondary logistic regression analysis will be conducted to examine treatment initiation by the end of the 6-month follow-up using worst case imputation of missing outcome to test robustness of any effects. Additional secondary analyses to demonstrate treatment robustness will be treatment initiation by the 1-month and 3-month follow-ups.

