Exploratory Analyses: Explore the effect of CBT-TS in increasing the initiation of and retention to other non-pharmacological pain treatments among Veterans receiving opioid analgesics for chronic pain. For treatment initiation and treatment retention, we will employ the same approach as described in Aims 1 and 2. As an additional set of exploratory analyses and consistent with an experimental therapeutics approach, we will explore beliefs as potential mediators of treatment initiation. Structural equation modeling (SEM) will be used to conduct these analyses. Latent variables (BHS, PTWS, PSEQ, PCS, TSK, MBQ, BQ) will be constructed to capture beliefs about opioids, treatment, beliefs that pain can be reduced, and hope. These variables will be included as potential mediators between condition and treatment initiation by month 6 as well as pain and opioid clinical outcomes at month 6. Prior to testing the mediation model, the direct effects of condition on treatment initiation, pain, and opioid outcomes at month 6 will be examined in one model. Next, the latent belief factors at month 3 will be included as mediators. All models will be conducted including relevant baseline autoregressors. Measurement invariance across conditions and across treatment initiation status will be established for the month 3 latent belief factors. All models will be re-analyzed using manifest variables instead of latent variables to test for model robustness. Any differences will be discussed. We will also explore variables such as gender, baseline dose, age, race/ethnicity, parent station type (1a-c, 2, 3) as potential moderators of treatment effect to drive further study.

Analysis in Support of Specific Aims for Optional Add-on Study: **Aim 1 Hypothesis:** African American participants receiving CBT-TS will be significantly more likely to initiate psychosocial pain treatment than African American participants in the control condition, compared to rates of treatment initiation in the rest of the sample. Treatment initiation of psychosocial pain treatment will be treated as a binary outcome variable (0|1). A Cox Proportional Survival Analysis⁹⁷ will be conducted to examine treatment initiation by the 6-month follow-up. Race will be dummy coded (0 = African American, 1 = other) and included as an independent variable as well as moderator of treatment condition.

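### The Aim 3 robustness analysis repeats the month-6 primary contrast, plans no month-3 contrast, and cannot test the time shape the model implies

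*Combined protocol and SAP*

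**What the plan says.** Section 5.1 sets the visits: "Follow-up assessment will occur 1-, 3-, and 6-months post-treatment". Section 5.7 lists the Aim 3 endpoints: "The outcomes will be pain severity, pain interference, physical functioning, opioid dose, and risk of misuse". The model for all five is given as "Treatment condition, follow-up time (centered on 6-month follow-up), and a condition by time interaction term will be included as predictors", together with the baseline value. With time centred at month 6, the condition coefficient is the model's treatment difference at month 6.

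The robustness step follows in 5.7 as "centering time at the 1-month and 6-month follow-ups, allowing for examination of treatment differences at these timepoints", and the Abstract has the same sentence: "Additional secondary analysis to demonstrate treatment robustness will involve centering time at the 1-month and 6-month follow-ups".

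Two other parts of 5.7 bear on this:

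- The parallel sentence for Aim 1 names the two non-primary visits: "Additional secondary analyses to demonstrate treatment robustness will be treatment initiation by the 1-month and 3-month follow-ups".
- In the exploratory mediation analysis, month 3 appears only for beliefs ("Next, the latent belief factors at month 3 will be included as mediators"). The step before it uses month-6 outcomes: "the direct effects of condition on treatment initiation, pain, and opioid outcomes at month 6 will be examined in one model".

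The plan does not call time linear or continuous. It also mentions no categorical coding of visit, no curvature term and no check of time shape.

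**The concern.** There are two linked problems.

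The first is textual. A robustness analysis should differ from the analysis it supports. Half of this one is the primary contrast, while a visit at which all five outcomes are available gets no contrast.

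The second concerns what re-centring can do. Moving the origin of time changes which point on the fitted line the condition coefficient describes. It does not change the line. If the treatment effect does not follow a straight line over months 1, 3 and 6, the month-6 estimate is shifted by the earlier visits, and no amount of re-centring will show it. At stake are the month-6 conclusions for five clinical outcomes and the account of when any effect appears.

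**Working it through.** **The plan's own figure.** The only stated number bearing on Aim 3 is the sample size: 250 × 1.20 = 300, which reproduces. The plan gives no effect sizes by visit, SDs or correlations, so the effect patterns and correlations below are assumptions.

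**Step 1: redundancy.** One simulated data set of 300 participants was fitted three times, with time centred at 1, 3 and 6 months. All three fits had log-likelihood -1133.1363 and interaction 0.0326. The condition coefficients were 0.2495, 0.3148 and 0.4127. These are three points on one line, and the last is the primary test itself.

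**Step 2: weights under a straight line.** Let d1, d3 and d6 be the treatment differences at the three visits. With complete data and compound symmetry, the estimate at time t0 gives the visit at time t the weight

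1/3 + (t0 - m)(t - m)/S,

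where m = (1 + 3 + 6)/3 = 3.333 and S = 5.444 + 0.111 + 7.111 = 12.667.

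| Estimate at | weight on d1 | weight on d3 | weight on d6 |
|---|---|---|---|
| month 1 | 0.763 | 0.395 | -0.158 |
| month 3 | 0.395 | 0.342 | 0.263 |
| month 6 | -0.158 | 0.263 | 0.895 |

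A random intercept plus slope gave the same weights. An AR(1) case gave -0.109, 0.182 and 0.927 at month 6.

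**Step 3: bias at month 6.** Subtracting d6 from the last row gives -0.158 d1 + 0.263 d3 - 0.105 d6 = 0.263 × [d3 - (0.6 d1 + 0.4 d6)]. This is zero whenever d3 lies on the line joining d1 and d6.

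| Assumed d1 / d3 / d6 (SD) | line at month 6 | bias |
|---|---|---|
| 0.35 / 0.35 / 0.35 | 0.350 | 0 |
| 0.1 / 0.3 / 0.6 | 0.600 | 0 |
| 0.1 / 0.4 / 0.4 | 0.447 | +0.047 |
| 0 / 0 / 0.4 | 0.358 | -0.042 |
| 0.1 / 0.4 / 0.1 | 0.179 | +0.079 |
| 0.4 / 0 / 0 | -0.063 | -0.063 |
| 0 / 0.4 / 0 | 0.105 | +0.105 |

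Under the AR(1) case the range narrows to -0.044 to +0.073.

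**Step 4: effect on the test.** Take 125 per arm, correlation 0.5 and two-sided 0.05. The month-6 variance under the line is 0.947 of the categorical one, so the standard error is √(2/125 × 0.947) = 0.123.

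- Pattern 0/0/0.4: power is 82.8% with the line and 88.5% with categorical visit.
- Pattern 0.1/0.4/0.4: power is 95.3% and 88.5%.
- Pattern 0/0.4/0: the month-6 test rejects in 13.7% of trials with the line, against a nominal 5%.

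**Step 5: price of categorical visit.** The variance ratio (line to categorical, correlation 0.5) is 0.947 at month 6 and 0.671 at month 3. The standard errors therefore rise by 1/√0.947 = 1.03 and 1/√0.671 = 1.22.

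**The case against.** The best reply is that this is a probable slip, 6 written for 3, in a secondary sentence of an aim that section 6.0 treats as a secondary, downstream goal. Section 3.0 states no month-3 hypothesis for Aim 3. Linear-time multilevel models are legitimate, and the exploratory mediation work estimates month-6 effects without a time line.

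Much of this stands. The slip reading is plausible given the Aim 1 wording, but the sentence appears twice and as written defines the wrong analysis. The mediation step is a partial check only: it is exploratory, does not name physical functioning and gives no month-3 contrast.

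A reader might also infer four stronger things that the documents do not support:

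- **That month-3 data are discarded, or that a re-centred estimate ignores its own visit.** All three visits enter every estimate. Month 6 carries 0.895 of its own estimate and month 3 carries 0.342. Under a line, the month-3 estimate is even recoverable as 0.6 × month-1 estimate + 0.4 × month-6 estimate. What is missing is a planned contrast.
- **That the plan specifies a straight line.** This is inferred from one centred term and one interaction.
- **That a straight-line effect is unlikely.** The conceptual model in section 2.0 gives a causal chain but no time course, and gradual accumulation fits it too.
- **That the month-6 result is seriously distorted.** Every bias in the table is below one standard error (0.123), and the largest comes from an effect present only at month 3, which the plan does not predict.

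**Conclusion.** The point holds in two parts of different certainty. The textual part needs no assumption: the month-6 robustness analysis is the primary test, and no month-3 contrast is planned for any Aim 3 outcome. Nor does it need an assumption to say that re-centring cannot test the model it re-expresses.

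The modelling part is conditional. If time is one linear term, the month-6 contrast carries a bias of 0.263 × [d3 - (0.6 d1 + 0.4 d6)] with complete data and compound symmetry. That is about -0.06 to +0.11 SD in the non-linear patterns tried, and zero for a linear effect. The size depends on assumed patterns and covariance. It justifies a correction before unblinding, but does not put the Aim 3 analysis in serious doubt.

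**What to change.** For Aim 3, in 5.7 and in the Abstract, replace the robustness sentence and the single centred time term with one model: visit as a categorical factor (1, 3 and 6 months), condition-by-visit terms, the baseline value and unstructured covariance. Name month 6 as the primary contrast and months 1 and 3 as secondary contrasts. The month-6 contrast then does not depend on the time pattern.

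This changes the main model for five outcomes, so it is more than a wording edit, though it uses the same data and mixed-model framework. It costs two more mean parameters and the standard-error increases in step 5.

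If the sponsor keeps the linear model as primary, the minimum is to say that time is linear, change the second robustness time point from 6 months to 3 months in both places, and report the categorical-visit model as the robustness analysis. Changing the month alone restores the contrast but leaves the time shape untested, since only about a third of a line-based month-3 estimate comes from month 3.
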